## 6.2. On therapy evaluations during induction phase

**Cycles 1-8: before starting each cycle (+/- 3 day window):**

The following assessments will be performed prior to each cycle of pembrolizumab.

- Interval History
- ECOG performance status evaluation
- Structured adverse event assessment
- Concomitant medication review
- Physical exam
- Complete blood count with differential
- Acute care & mineral panels (includes Na, K, Cl, CO2, creatinine, glucose, BUN, phosphorus, magnesium, albumin, and calcium)
- Total protein, CK, Uric Acid, and LDH
- Hepatic panel (includes alkaline phosphatase, ALT, AST, total bilirubin, and direct bilirubin)
- Reticulocyte count

- PT, PTT, fibrinogen
- Pregnancy test for females of childbearing potential

### 6.3. Clinical Assessments

Clinical endpoints on this trial are defined as below:

**Table 7: Clinical Endpoints**

Outcome	Included Patients	Point of Measurement	Definition
Feasibility	All	Interim Analysis/Safety Follow-Up Visit (see Section 6.5.1)	Descriptive summary of all adverse events (number, severity and duration of adverse events) according to NCI-Common Terminology Criteria for Adverse Events (CTCAE) v4.0
Efficacy	All	Following cycles 2, 4, 6, 8 and at progression/off-study time-point	Descriptive summary of conventional response criteria as described in Appendix A. In addition any clinical information regarding MRD status (eg: flow cytometry, cytogenetics, PCR) will be captured at these time-points.
Time to first response	Responders (mCR, mCRi,, CR, CRi, PR)	As above	Defined as time from start of study to initial achievement of first response.
Time to best response	As above	As above	Defined as time from start of study to initial achievement of best response.
Duration of response	As above	As above	Defined as time from initial achievement of response to loss of response.
Duration of best response	As above	As above	Defined as time from initial achievement of best response to loss of best response.
Overall survival	All	Entry onto trial	Death from any cause

**Bone marrow examinations for clinical response assessment will be performed pre-treatment and after cycles 2, 4, 6 and 8 (or the progression/off-study time-point).** Bone marrows after cycles 2, 4, 6 and 8 may be performed anytime in the week prior to the next cycle of Pembrolizumab (*ie:* the “after cycle 2” marrow may be performed prior to the pembrolizumab dose on day 1 of cycle 3 or anytime in the preceding week). Assessments will include clinical pathological assessment by morphology, flow cytometry and cytogenetics. An additional bone marrow for research purposes may be performed on or around day 8 of cycle 1. Additional bone marrows may be done after cycle 8, until progression as clinically indicated.

### 6.4. On therapy evaluations during optional continuation phase

Patients treated on the continuation phase will ordinarily be evaluated, including Structured adverse event assessment, as described in section 6.2, every 4 cycles (*ie:* every 12-13 weeks).

## 6.5. Post-Induction Treatment Follow-Up

### 6.5.1. Safety Follow-Up Visit (SFV)

The mandatory Safety Follow-Up Visit should be conducted after the eighth cycle of treatment (ie: end of induction phase), or (for patients discontinuing therapy prior to this point) approximately 30 days after the last dose of trial treatment or before the initiation of a new anti-cancer treatment, whichever comes first. All AEs that occur prior to this Safety Follow-Up Visit should be recorded. Subjects with a persistent treatment related AE will be followed until the resolution of the AE or until the beginning of a new anti-neoplastic therapy, whichever occurs first. No new adverse event information will be collected after this safety follow-up visit.

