### **5.9. Optional Continuation Phase after Eight Cycles of Pembrolizumab**

As described in section 5.1 this pilot study is intended to offer a total of eight doses of pembrolizumab on every three weekly cycles with decitabine given on alternative cycles as initial induction therapy.

In the event that a patient achieves a response of mCR, mCRi, CR, CRi, PR or SD (see Appendix A) at the end of cycle 8 assessment then additional cycles of pembrolizumab and decitabine therapy will be offered. These additional cycles will be given according to the same schedule (see section 5.1) with the below exceptions. Pembrolizumab in cycle 9 (ie: first cycle of continuation phase) may be delayed up to 7 days to allow post-induction phase staging to be completed. No more than 35 cycles (ie: two years) of therapy will be offered. Decitabine 20 mg/m^2 will be given for not more than ten consecutive days every six weeks and may be prescribed and supplied by non-study physician.

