### 9.1.1. Timing

The AE reporting period for this study begins when the patient takes the first dose of study drug and ends with the safety follow-up visit. If an SAE is present at the safety follow-up visit or within 30 days of the last dose of study drug (whichever is later), it should be followed to resolution or until the Investigator assesses the subject as stable, a new anticancer therapy is initiated, or the subject is lost to follow-up or withdraws consent. Resolution/stable means the subject has returned to baseline state of health or the Investigator does not expect any further improvement or worsening of the event.

All adverse events will be recorded at each examination on the Adverse Event case report forms/worksheets from the time the consent form is signed through the safety follow-up visit.

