## APPENDIX G: Scheduled Clinical Assessments

Trial Period:	Screening Phase	Induction Phase Treatment (Assessment at end of cycle...)								Post-Induction	
		1	2	3	4	5	6	7	8	SFV / Off-study Visits	Contin. Phase (q3mo)
Pre-screening and Consents	X										
Inclusion/Exclusion Criteria	X										
Demographics and Full Medical History	X										
Interval Medical History		X	X	X	X	X	X	X	X	X	X
Focused Physical Exam		X	X	X	X	X	X	X	X	X	X
ECOG Performance Status	Baseline	X	X	X	X	X	X	X	X	X	X
Structured Review of Adverse Events	Baseline	X	X	X	X	X	X	X	X	X	X
Prior and Concomitant Medication Review	X	X	X	X	X	X	X	X	X	X	X
Trial Treatment Administration Log		X	X	X	X	X	X	X	X		
Therapy Response Assessment	X		X		X		X		X	X	X
Bone Marrow Examination* (flow cytometry, morphology)	X		X		X		X		X		
Cytogenetics (bone marrow)	X		If+ @BL		If+ @BL		If+ @BL		X		
Pregnancy Test -- Urine or Serum $\beta$ -HCG	W/in 72 hours of first dose.	X	X	X	X	X	X	X	X	X	X
Acute Care, Mineral and Hepatic Panels	W/in 14 days of first dose	X	X	X	X	X	X	X	X	X	X
Total protein, CK, Uric Acid, LDH, PT, PTT, Fibrinogen, CBC w/ diff, Reticulocyte, Type&Screen.	X	X	X	X	X	X	X	X	X	X	X
CMV IgG, IgM and PCR, HIV serology, Hepatitis serologies,	X										
Thyroid Function (T3, FT4 and TSH), EKG, HLA typing, Urinalysis	X										
Peripheral Blood Flow Cytometry (T/B/NK and AML)	X		X		X		X		X		

"If + @ BL" = Cytogenetics will be checked after cycles 2, 4 and 6 only if abnormal at baseline.

\* = an additional bone marrow examination assessment will be performed on cycle 1 day 8 (+/- 3 days).

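### New adverse event collection stops at a visit placed at the end of induction, which conflicts with the adverse event reviews scheduled in continuation and, for some patients, with the 30 days of monitoring promised after treatment

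*Combined protocol and SAP*

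**What the plan says.** **Where collection ends.** Section 6.5.1 places the safety follow-up visit after cycle 8 for patients who complete induction. For those who stop earlier it falls about 30 days after the last dose, or before a new anti-cancer treatment if that comes first. It then states: "No new adverse event information will be collected after this safety follow-up visit". In Section 9.1.1 one sentence says the reporting period "ends with the safety follow-up visit". Another has AEs recorded "from the time the consent form is signed through the safety follow-up visit". The two differ on when the period starts but agree on when it ends. Section 9.2 counts ten scheduled evaluation time-points, none of them in continuation.

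**What happens after that visit.**
- Section 5.9 offers both drugs beyond cycle 8 to patients with at least stable disease: "No more than 35 cycles (ie: two years) of therapy will be offered".
- Section 6.4: "Patients treated on the continuation phase will ordinarily be evaluated, including Structured adverse event assessment", every four cycles.
- Appendix G marks the row "Structured Review of Adverse Events" in the three-monthly continuation column and in the column shared by the safety and off-study visits.
- Sections 5.8.2 and 6.5.3 promise each subject 30 days of AE monitoring after the end of treatment.

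**What survives the cut-off.** Persistent treatment-related AEs are followed (6.5.1). Serious AEs (SAEs) present at the visit, or within 30 days of the last dose if later, are followed (9.1.1). SAEs and events of clinical interest (ECIs) are reportable to 90 days after cessation, subject to limits tied to new therapy (9.4, 9.6). Related SAEs are reportable at any time (9.4), and related events go to the data and safety monitoring board (9.0). Detected AEs go into the medical record (9.2).

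**The concern.** Staff are told to assess AEs in patients still being dosed and also told that no new AE information is collected. If the sentence in Section 6.5.1 is followed literally, new events that are neither serious nor ECIs drop out of the trial data during continuation. Section 2.7 describes the combination as untested and makes descriptive AE data the substance of the feasibility endpoint.

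Section 9.8 foresees publications at 1 and 2 years from the start of treatment. No section says whether events recorded after the visit belong in them. If those reports describe safety, a reader could take missing continuation events for absence of toxicity.

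**Working it through.** **Inputs.** Cycle length 21 days and eight induction cycles (5.1). Pembrolizumab on day 1 of each cycle; decitabine ordinarily ending on day 19 of cycles 1, 3, 5 and 7, with a window of 3 days either way (5.3). Maximum 35 cycles, and cycle 9 may be delayed by up to 7 days for post-induction staging (5.9). Study day = (cycle − 1) × 21 + day of cycle.

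**The plan's own figures.** 35 × 21 = 735 days = 105 weeks = 2.01 years, which agrees with two years in Section 5.9. Four cycles = 84 days = 12 weeks, which agrees with Section 6.4. Time-points in Section 9.2: 1 + 8 + 1 = 10, as stated.

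**Where the visit falls.** Cycle 8 ends on day 8 × 21 = 168. Cycle 9 day 1 is day 169, or up to day 176 with the delay. No day is given for a completer's visit. That it precedes cycle 9 is an inference: Section 6.5.1 equates it with the end of induction, and Section 5.9 lets cycle 9 wait for staging.

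**Continuation dosing after the cut-off (ceiling, one patient).** 35 − 8 = 27 cycles; 27 × 21 = 567 days; 567/735 = 77%.

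**Scheduled AE reviews after the cut-off.** Every four cycles counted from cycle 8: after cycles 12, 16, 20, 24, 28 and 32, which is 6. Adding the off-study visit gives at most 7.

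**The 30 days after treatment, by type of patient.**
- *Continuers:* the last dose comes after the visit, so all 30 days are uncovered.
- *Completers who do not continue:* last pembrolizumab is on day 7 × 21 + 1 = 148. Last decitabine is on day 6 × 21 + 19 = 145, or 148 with the 3-day window. The last dose is therefore day 148. If the 30 days run from the last dose, they end on day 178; a visit on day 168 leaves 178 − 168 = 10 days uncovered, and a visit on or after day 178 leaves none. If they run from the end of cycle 8, they end on day 198; a visit on day 168 leaves 198 − 168 = 30 days uncovered. The protocol does not define the end of treatment, so both readings stand.
- *Early stoppers:* with the visit v days after the last dose, the gap is max(0, 30 − v). It is zero at about 30 days. It is positive only if the visit is held early, because the off-study visit serves as the safety visit (6.5.2) or a new anti-cancer treatment starts (6.5.1).

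**What cannot be computed.** The Precis gives an average treatment length of six months, about 182.6 days, and it is tempting to subtract 168. That is not valid. Exposure after the cut-off is max(0, T − 168), where T is a patient's time on treatment, and its mean does not follow from the mean of T. As a hypothetical, let half the patients stop at day 84 and half at day 281. The mean is (84 + 281)/2 = 182.5 days, yet 281 − 168 = 113 of 365 treated days (31%) fall after the cut-off. The number entering continuation is not stated either. It lies between 0 and 10, because a replaced patient stops before the fourth pembrolizumab dose (5.10).

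**The case against.** The strongest reply is that little is lost. Table 7 measures feasibility at the interim analysis and the safety follow-up visit, and Section 8.3 confines the safety endpoint to the eight induction cycles, so no planned primary analysis changes. SAEs and ECIs stay reportable, and ECIs must go on the AE case report forms (9.6). Section 10.6 has data abstracted from Clinical Center and home-physician notes. Section 9.8 lets notable toxicity in individual patients be published at any time. Section 6.4 is the specific rule for patients on continuation and could be read as overriding a sentence that sits under post-induction follow-up. Section 9.2 also counts the safety visit separately from the assessment after cycle 8, so the visit may fall somewhat later than day 168.

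Most of this stands and limits the point to new events that are neither serious nor ECIs. It does not remove the conflict. Section 9.1.1 repeats the cut-off as a general rule, so Section 6.4 cannot simply be presumed to override it. The 90-day windows themselves contradict a statement that no new AE information is collected. A visit held a few days later would still precede nearly all continuation dosing in a patient treated to cycle 35. A note in a medical record does not settle whether the event is tabulated.

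**Conclusion.** The contradiction is in the text and should be reconciled; severity is minor to should-fix. Literal adherence would lose new non-serious, non-ECI events in 0 to 10 continuing patients, with a ceiling of 27 of 35 cycles (77%) for one patient dosed to cycle 35. The uncovered part of the 30 days is all 30 for continuers. For completers who do not continue, it is up to 10 or up to 30 days, depending on how the end of treatment is defined. For early stoppers it is normally zero. The conclusion assumes that the completer's visit precedes cycle 9, and it matters only if the 1- and 2-year reports describe safety.

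A reader might infer more than the documents support:
- *That serious toxicity in continuation goes unseen.* Sections 9.0, 9.4 and 9.6 say otherwise.
- *That the primary result or the stopping rule is compromised.* Both are confined to induction.
- *That the 30-day promise fails for everyone.* For early stoppers seen at about 30 days, the two windows agree.
- *That the average loss can be estimated from the six-month figure.* It cannot, as shown above.

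**What to change.** Limit the closing sentence of Section 6.5.1, and the end of the AE period in Section 9.1.1, to the induction summary. State that AEs recorded in continuation and in the 30 days after the end of treatment (to be defined), and SAEs and ECIs for the full windows in Sections 9.4 and 9.6, are trial data tabulated separately from that summary. Reconcile Sections 5.8.2, 6.4, 6.5.1, 6.5.2, 6.5.3, 9.1.1, 9.2, 9.4, 9.6 and Appendix G with this. Leave Table 7's induction summary and the Section 8.3 rule as they are.

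In the later reports, add one descriptive table of post-visit events already on record (continuation reviews, medical record, SAE and ECI reports). Give patients and continuation cycles as denominators, and state that non-serious ascertainment after the visit may be incomplete.

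The cost is a wording change, AE abstraction for at most 10 patients, and one table. No new visits are needed, since Section 11.3 puts the study in data analysis only from March 15, 2019. For the same reason the change cannot recover events that were never elicited, so the table may understate non-serious events.

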### 9.4. Company Reporting

#### **Reports to Merck:**

A SAE is any AE occurring at any dose or during any use of Merck’s product that:

- Results in death;
- Is life threatening;
- Results in persistent or significant disability/incapacity;
- Results in or prolongs an existing inpatient hospitalization;
- Is a congenital anomaly/birth defect;
- Is a new cancer (that is not a condition of the study);
- Is associated with an overdose;
- Is an other important medical event

Any SAE, or follow up to a SAE, including death due to any cause other than progression of the cancer under study that occurs to any subject from the time the consent is signed through 90 days following cessation of treatment, or the initiation of new anti-cancer therapy, whichever is earlier, whether or not related to Merck product, must be reported within 24 hours to the sponsor and within 2 working days to Merck Global Safety.

Additionally, any SAE, considered by an investigator who is a qualified physician to be related to Merck product that is brought to the attention of the investigator at any time outside of the time period specified in the previous paragraph also must be reported immediately to the Sponsor and to Merck.

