**SAE reports and any other relevant safety information are to be forwarded to the Merck Global Safety [contact]**

A copy of all 15 Day Reports and Annual Progress Reports is submitted as required by FDA, European Union (EU), Pharmaceutical and Medical Devices agency (PMDA) or other local regulators. Investigators will cross-reference this submission according to local regulations to the Merck Investigational Compound Number (IND, CSA, etc.) at the time of submission. Additionally investigators will submit a copy of these reports to Merck & Co., Inc. (Attn: Worldwide Product Safety; [contact]) at the time of submission to FDA.

All subjects with serious adverse events must be followed up for outcome.

Non-serious Events of Clinical Interest will be forwarded to Merck Global Safety and will be handled in the same manner as SAEs.

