**Additional adverse events:** A separate guidance document has been provided entitled “Event of Clinical Interest Guidance Document” (previously entitled, “Event of Clinical Interest and Immune-Related Adverse Event Guidance Document”). This document can be found in Appendix C and provides guidance regarding identification, evaluation and management of ECIs and immune-related AEs.

ECIs (both non-serious and serious adverse events) identified in this guidance document from the date of first dose through 90 days following cessation of treatment, or 30 days after the initiation of a new anticancer therapy, whichever is earlier, need to be reported within 24 hours to the Sponsor and within 2 working days to Merck Global Safety. (Attn: Worldwide Product Safety; [contact]), regardless of attribution to study treatment, consistent with standard SAE reporting guidelines.

Subjects should be assessed for possible ECIs prior to each dose. Lab results should be evaluated and subjects should be asked for signs and symptoms suggestive of an immune-related event. Subjects who develop an ECI thought to be immune-related should have additional testing to rule out other etiologic causes. If lab results or symptoms indicate a possible immune-related ECI, then additional testing should be performed to rule out other etiologic causes. If no other cause is found, then it is assumed to be immune-related.

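### SAEs and ECIs that begin after the safety follow-up visit must still be reported, but have no stated place in or beside the primary adverse event summary

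*Combined protocol and SAP*

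**What the plan says.** **The cut-off.** Table 7 (section 6.3) defines the feasibility outcome as a "Descriptive summary of all adverse events (number, severity and duration of adverse events"), graded by CTCAE v4.0. Its point of measurement is "Interim Analysis/Safety Follow-Up Visit". For patients who stop early, section 6.5.1 (Safety Follow-Up Visit) sets that visit at roughly day 30 after the last dose, or before new anti-cancer treatment, whichever is first. For those who finish induction, it falls after cycle 8. The section closes with "No new adverse event information will be collected after this safety follow-up visit". Section 9.1.1 agrees: the AE reporting period starts with the "first dose of study drug and ends with the safety follow-up visit".

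**The later duties.**
- Section 9.4: SAEs, related or not, are reportable from consent "through 90 days following cessation of treatment, or the initiation of new anti-cancer therapy, whichever is earlier". Deaths from progression of the leukemia are excepted.
- Section 9.4, next paragraph: an SAE judged related to pembrolizumab that an investigator learns of "at any time outside of the time period specified in the previous paragraph also must be reported immediately to the Sponsor and to Merck".
- Section 9.6: listed ECIs are reportable "from the date of first dose through 90 days following cessation of treatment, or 30 days after the initiation of a new anticancer therapy"; the sooner of the two limits applies. The same section requires ECIs to be entered on the AE case report forms.

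**Other relevant text.** Section 5.2.2 says pembrolizumab-associated events can appear months after dosing has ended. Sections 5.8.2 and 6.5.3 each give every subject 30 days of AE monitoring after treatment ends, with no cut-off at new therapy.

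**The concern.** The AE summary is the primary result, and section 8.1 states the primary hypothesis as safe co-administration of the two drugs. The plan's own account of pembrolizumab toxicity includes delayed onset, yet the summary is tied to a visit near day 30, while two other sections oblige the investigator to report new serious and immune events after it.

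The text therefore contains two instructions that cannot both be followed literally, and it does not say which governs the primary table. If the collection rule governs, a late immune event known to the sponsor and the drug company could be absent from the published safety summary. With ten planned patients (section 8.2), a single such event would matter to a reader judging the combination.

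**Working it through.** The plan states no figure for this gap, so there is none to reproduce. The check compares time windows.

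**Inputs.** Let T be the days from last dose to new anti-cancer therapy. Cessation of treatment is taken as the last dose.
- Visit day = min(30, T) (6.5.1)
- All-cause SAE limit = min(90, T) (9.4)
- ECI limit = min(90, T + 30) (9.6)
- Related SAE limit: none (9.4)
- Gap = limit minus the day on which AE collection ends

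**Results for a patient who stops during induction, with collection ending at the visit (days):**

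| T | Visit | SAE limit | SAE gap | ECI limit | ECI gap |
|---|---|---|---|---|---|
| 10 | 10 | 10 | 0 | 40 | 30 |
| 30 | 30 | 30 | 0 | 60 | 30 |
| 45 | 30 | 45 | 15 | 75 | 45 |
| 60 | 30 | 60 | 30 | 90 | 60 |
| 90 | 30 | 90 | 60 | 90 | 60 |
| none | 30 | 90 | 60 | 90 | 60 |

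With no new therapy, collection covers 30 of the 90 reportable post-dose days.

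**Sensitivity for T below 30.** Here the plan supports two readings. If collection stops at a visit held when new therapy starts, the ECI gap is (T + 30) − T = 30 days. If the 30-day monitoring in 5.8.2 and 6.5.3 applies regardless of new therapy, collection runs to day 30 and the ECI gap is (T + 30) − 30 = T days, which is 10 at T = 10. The all-cause SAE gap is 0 on either reading.

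**The visit day is not exact.** Section 6.5.1 says approximately 30 days, and section 6.5.2 lets the off-study visit double as the safety visit for patients who leave during the first eight cycles. An earlier visit would lengthen the gap if collection stops there.

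**Completers.** Patients who finish eight cycles and do not continue meet the same cut-off at their post-cycle-8 visit, so they face a similar gap. Patients in the continuation phase differ: section 6.4 and Appendix G schedule structured AE review for them.

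**Does any provision close the gap?**
- 6.5.1 follows persistent treatment-related AEs, which are already known.
- 9.1.1 follows SAEs present at the visit or within 30 days of the last dose, whichever is later.
- 9.4 adds "All subjects with serious adverse events must be followed up for outcome", which concerns outcome, not tabulation.
- 9.0 sends related AEs and SAEs to the DSMB.
- 9.8 plans publications after induction and at 1 and 2 years, without extending AE collection.

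None of these assigns a first-onset event after the visit to the Table 7 summary or to a companion table.

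**The case against.** The strongest reply is that late ECIs may reach the summary after all. Section 9.6 puts ECIs on the AE case report forms and runs their reporting to day 90, and Table 7 covers all AEs. No sentence says that an ECI on those forms is excluded. This stands in part. Exclusion is the direct reading of 6.5.1 and 9.1.1, but not the only one. What remains is that the plan leaves the matter unsettled.

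Second, a fixed window is a legitimate choice. Section 9.8 times the primary analysis to the end of induction, section 8.3 limits its safety endpoint to induction, and company reporting serves a different purpose. This also stands, and it is why the primary table and stopping rule should not be altered.

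Third, section 8.4 allows further descriptive analyses, and section 9.8 allows individual cases of notable toxicity to be published. Both are permissive; neither requires late events to be shown.

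A reader might infer that late toxicity goes unreported or is hidden. The documents do not support this: such events go to the sponsor and the drug company, and related ones to the DSMB. A reader might also treat the open-ended duty for related SAEs as an unlimited gap in surveillance. It is not, because it covers only events that come to the investigator's attention. It is passive reporting and should not be set beside the day counts as if it were active follow-up.

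**Conclusion.** The inconsistency is real and sits in current operative text. First-onset SAEs (other than deaths from progression) and ECIs arising after the safety follow-up visit are reportable, but have no stated place in or beside the primary summary.

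For early stoppers, the gap is about 60 days for both kinds of event without new therapy. With new therapy between day 30 and day 90, it is 0 to 60 days for SAEs and 30 to 60 for ECIs. With new therapy before day 30, it is 0 for all-cause SAEs and either T or 30 days for ECIs, depending on which monitoring rule applies. These figures assume that cessation means the last dose and that the visit falls on day 30 or, if earlier, on the day new therapy starts.

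It would go too far to conclude that events have been missed or that the primary result is wrong. The documents give neither a late-event rate nor a number of early stoppers. This is a reporting improvement that should be made, not a flaw that invalidates the analysis.

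**What to change.** 1. Keep the Table 7 summary through the safety follow-up visit as the primary table, and leave the section 8.3 stopping rule unchanged.
2. Add one listing, labelled as supplementary and as added after treatment ended, of SAEs and ECIs with onset after that visit. Include all patients who stopped during induction or completed it without continuing; restricting it to early stoppers would be selective.
3. Fill it from the 9.4 and 9.6 reports. For each event give grade, relatedness, days from last dose to onset, whether it is an SAE, an ECI or both (counted once), and whether onset followed new anti-cancer therapy.
4. Amend the closing sentence of 6.5.1 to except SAEs and ECIs reportable under 9.4 and 9.6.

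**Cost.** One listing and one sentence. No visit or new data are needed, because the reports are already required. Section 11.3 places the study in data analysis only, so the amendment aligns the text with existing duties and changes no conduct.

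**Downsides.** Attribution is harder once new therapy has begun. Late related SAEs depend on passive reports, so an empty listing would not show that none occurred. The listing holds only SAEs and ECIs, so its counts cannot be compared with those in the all-AE table.
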